2.2 Objectives

2.2.1 Primary objective

The primary objective is:

- To investigate efficacy of inhaled molgramostim on NTM sputum culture conversion to negative.

2.2.2 Secondary objective(s)

The secondary objectives are:

- To investigate efficacy of inhaled molgramostim on NTM sputum smear conversion to negative.
- To investigate efficacy of inhaled molgramostim on reduction of NTM bacterial load in sputum.
- To investigate efficacy of inhaled molgramostim on exercise capacity.
- To investigate efficacy of inhaled molgramostim on Subject Reported Outcomes.
- To investigate safety of inhaled molgramostim in subjects with NTM infection.

2.3 Sample Size

It was planned that 30 subjects will be enrolled. No formal sample size calculation was done as this is an initial pilot study.

2.4 Treatment Assignment and Randomisation

At the Baseline visit, all subjects found to be eligible according to the inclusion/exclusion criteria will be classified into the following treatment groups:

- Group 1: Subjects who remain sputum culture positive while currently on a multidrug NTM guideline based antimycobacterial regimen, which has been ongoing for at least 6 months prior to the Baseline Visit.
- Group 2: Subjects who remain sputum culture positive but have either stopped a multidrug NTM guideline based antimycobacterial regimen at least 28 days prior to Screening due to lack of response or intolerance, or never started such treatment.

Subjects successfully assigned to a subgroup will then start treatment with open-label molgramostim nebulizer solution.

3. STATISTICAL CONSIDERATIONS

3.1 Analytical Approach

Data analysis will be performed according to Southern Star Research's Standard Operating Procedures (SOPs).

The general analytical approach for all endpoints will be descriptive in nature. All summaries will present the data by treatment group as well as by all subjects combined.

Unless otherwise stated, the following statistical approaches will be taken:

Continuous variables: Descriptive statistics will include the number of non-missing values, mean, standard deviation (SD), median, minimum, and maximum. The minimum and maximum values will be presented to the same number of decimal places as recorded in the eCRF; mean, median, and SD will be presented to one more decimal place than the raw data.

Categorical variables: Descriptive statistics will include frequency counts and percentages per category. Percentages will be rounded to one decimal place, with the denominator being the number of subjects in the relevant population with non-missing data.

Multiplicity: As this is an exploratory study no adjustments for multiplicity will be applied.

Confidence intervals (CIs): CIs will be two-sided and will use 95% confidence levels. Any analyses requiring significance testing will use a two-sided test at the 5% significance level.

Unscheduled Visits Unscheduled visits will be excluded from summary tables.

3.2 Data Capture

3.2.1 Database

The primary method of data collection is via the study database, developed within the chosen Electronic Data Capture (EDC) platform, IBM Clinical Development. The database has been designed based on the final protocol, the system/core configuration, electronic Case Report Form (eCRF) specifications and/or mock eCRF and consistency check specifications.

Data will be entered directly into the EDC system.

Site-collected data will be entered directly from source notes at the site and will be verified by Clinical Research Associates (CRAs) to ensure data integrity.

This study also includes subject reported outcomes collected through ePRO entry within the EDC.

Refer to the Data Management Plan for further details.

3.2.2 *Third Party Data*

3.2.2.1 *Safety Laboratory*

Central safety laboratory data will be received from BARC Global Central Laboratory as specified in the BARC Data Transfer Specification. Data transfers are being processed on a monthly basis throughout the study, with each transfer being reconciled against the CRF data.

The final data transfer will be incorporated into the End of Study analysis once the final transfer has been received, reconciled and any issues are considered resolved.

No conversion of laboratory data will be performed.

3.2.2.2 *Anti-GM-CSF*

Anti-GM-CSF data will be received from Bioagilytix Europe GMBH as specified in the Bioagilytix Data Transfer Specification. Two data transfers will take place. The first transfer will occur following analysis of samples up to Visit 5 for the first six subjects and the second transfer will occur at End of Study.

The End of Study data transfer will be incorporated into the End of Study analysis once the transfer has been received, reconciled and any issues are considered resolved.

3.2.2.3 *Microbiology Analysis (Australia)*

Microbiology analysis of samples from Australian sites will be analysed and reported by Sullivan Nicolaides Pathology (SNP) as specified in the SNP Data Transfer Specification. Data transfers are being processed on a monthly basis throughout the study, with each transfer being reconciled against the CRF data.

The final data transfer will be incorporated into the End of Study analysis once the final transfer has been received, reconciled and any issues are considered resolved.

3.2.2.4 *Microbiology Analysis (UK)*

Microbiology analysis of samples from UK sites will be analysed and reported by Royal Brompton Hospital (RBH) as specified in the RBH Data Transfer Specification. Data transfers are being processed on a monthly basis throughout the study, with each transfer being reconciled against the CRF data.

The final data transfer will be incorporated into the End of Study analysis once the final transfer has been received, reconciled and any issues are considered resolved.

3.3 Statistical Programming

3.3.1 CDISC

3.3.1.1 SDTM

All study datasets will be structured according to Clinical Data Interchange Standards Consortium (CDISC) Study Data Tabulation Model (SDTM) conventions as detailed in Table 1.

Table 1: SDTM Specifications and Deliverables

Deliverable	Specification
SDTM convention	SDTM Model v1.4, SDTMIG v3.2
CDISC Validator	Pinnacle21 v2.2.0 or later
SAS Version	V 9.4, vlatin1
SDTM Export Datasets	*.xpt
SDTM Annotated CRF	Required, aCRF.pdf in searchable pdf with required colour annotation
Define.XML	Required, v2.0.0
Study Data Reviewer's Guide	Required, sdrg.pdf

3.3.1.2 ADaM

Analysis datasets will be structured according CDISC Analysis Data Model (ADaM) conventions as detailed in Table 2.

Table 2: ADaM Specifications and Deliverables

Deliverable	Specification
ADaM convention	ADaMIG v1.1
CDISC Validator	Pinnacle21 v2.2.0 or later
SAS Version	V 9.4, vlatin1
ADaM Export Datasets	*.xpt
Define.XML	Required, v2.0.0
Analysis Data Reviewer's Guide	Required, adrg.pdf (paper size - Letter)

3.3.2 Study Terminology

Study-specific standard terms are detailed in Table 3.

Table 3: Study CDISC Terminology

Subject Elements	Screen (SCRN) Molgramostim (MOLG) Follow-Up (FU)
Epochs	SCREENING OPEN LABEL TREATMENT FOLLOW-UP
Treatment Arms	GROUP 1 GROUP 2
Visit Numbers / Visits	
SCREENING EPOCH
 
1.0 Screening
 
TREATMENT EPOCH
 
2.0 Baseline Visit*
 
3.0 Week 4
 
4.0 Week 8
 
5.0 Week 12
 
6.0 Week 16
 
7.0 Week 20
 
8.0 Week 24
 
9.0 Week 28
 
10.0 Week 32
 
11.0 Week 36
 
12.0 Week 40
 
13.0 Week 44
 
14.0 Week 48
 
888 Early Discontinuation
 
999 End of Study
 
FOLLOW-UP EPOCH
 
15.0 Follow Up Visit
 
Unscheduled visits: x.n where x is the visit number of the closest previous scheduled visit and n is the sequence number of the unscheduled visit, restarting at 1 after each scheduled visit. EPOCH will be assigned according to the epoch of the closest previous visit.
 
* “Baseline Visit” will be used when referring to Visit 2. The term “Baseline” will also be used as detailed in 3.3.3.

3.3.3 **Baseline**

For sputum data, baseline will be derived from the combined pre-treatment visits (i.e. Screening and Baseline), where at least one positive sample will be assigned as positive as baseline. For gradings, the most severe/highest grade will be used.

For all other parameters, baseline will be defined as the last available assessment prior to first study drug administration.

3.3.4 **Change from Baseline**

Absolute change from Baseline will be calculated as:

$$\text{Absolute change from baseline} = (\text{postbaseline value}) - \text{baseline value}$$

3.3.5 **Listings, Tables and Figures**

Listings, tables and figures will be delivered as individual .rtf files in accordance with the mock listings, tables and figures.

Data listings will present all data, with subjects grouped by Group.

Tabulations will summarise data by Group and Total.

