| Dispense trial drug       |           | X                 | X                | X                | X                | X                 | X                 | X                 | (X)               | X                 | (X)               | X                 |                   |                   |                   | (X)                            |
| Return of used trial drug |           |                   | X                | X                | X                | X                 | X                 | X                 |                   | X                 |                   | X                 |                   | X                 |                   | (X)                            |
| Compliance                |           |                   | X                | X                | X                | X                 | X                 | X                 |                   | X                 |                   | X                 |                   | X                 |                   | (X)                            |
| AEs                       |           | X                 | X                | X                | X                | X                 | X                 | X                 | X                 | X                 | X                 | X                 | X                 | X                 | X                 | X                              |

Abbreviations: 6MWT= 6-minute walk test; AE=adverse event; CT= Computed tomography; DLCO= Diffusion capacity of the lung for carbon monoxide; ECG= electrocardiogram; GM-CSF=granulocyte macrophage colony stimulating factor; GRH=Global rating of health; LRTI-VAS= lower respiratory tract infection-visual analogue scale; QoL-B= Quality of Life- Bronchiectasis

a Procedures marked with brackets should be performed as necessary.

b 6MWT includes assessment of SpO2 and Borg CR10 score for dyspnea before, during (SpO2) and after (Borg) the test.

c Three samples, preferably on consecutive days, will be collected. All samples collected at V9, V11 and V13 will home collected.

d Sample to be taken before dosing at the site.

e A chest X-ray not a study requirement. But if subjects have a chest X-ray during the study period as part of the local routine clinical practice, the results from the X-ray will be recorded.

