At each visit (Visits 1-15), sputum samples for staining and microscopy, and microbiological culture will be collected. If required, induced sputum may be obtained according to local standards. On the days of clinic visits (Visits 1, 2, 3, 4, 5, 6, 7, 8, 10, 12, 14 and 15), subjects will be asked to collect two additional sputum samples at home, preferably on the consecutive days after the site visit. On the days of the telephone contact visits (Visits 9, 11 and 13), three sputum samples will be collected at home, preferably on consecutive days.

Any AEs will also be collected at Baseline and all subsequent visits (Visits 2-15). At all clinic visits a pregnancy test/contraceptive check will be conducted, changes in concomitant medication, measurement of body weight and an assessment of DLCO will be performed. A computed tomography (CT) scan will be conducted at Baseline (Visit 2) if not performed within 6 months prior to Baseline. If DLCO drops by at least 20% at two consecutive visits the CT scan may be repeated. A CT scan can be performed after 48 weeks of treatment if this is a part of the local routine clinical practice.

A physical examination and an electrocardiogram (ECG) will be performed at Screening and Weeks 24 and 48 (Visits 1, 8 and 14) and vital signs will be collected at Screening, Baseline, and Weeks 4, 12, 24, 32, 40 and 48 (Visits 1, 2, 3, 5, 8, 10, 12 and 14). Spirometry will be conducted at Baseline and at Weeks 12, 24, 32, 40 and 48 (Visits 2, 5, 8, 10, 12 and 14). A 6MWT will be conducted at Baseline, at Weeks 12, 24 and 48 and at the 12-week follow-up visit (Visits 2, 5, 8, 14 and 15). Blood samples for safety laboratory testing will be taken at Screening, Baseline, and at Weeks 4, 12, 24, 32, 40, 48 and at the 12-week follow-up visit (Visits 1, 2, 3, 5, 8, 10, 12, 14, 15). Anti-GM-CSF will be assessed at Baseline, at Week 4, 12, 24, 32, 48 and at the 12-week follow-up visit (Visits 2, 3, 5, 8, 10, 14 and 15). Patient reported outcomes (QoL-B, LRTI-VAS and GRH) will be assessed at Baseline and at all post Baseline clinic visits (Visits 2, 3, 4, 5, 6, 7, 8, 10, 12, 14 and 15). For subjects having a chest X-ray during the study period as part of the routine local clinical practice, the results from the X-ray will be recorded.

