Participating subjects will be encouraged to contact the clinic between visits if they experience adverse events (AEs), worsening of their condition or have any other concerns. If needed, unscheduled visits will be conducted at investigator's discretion.

A schedule of study assessments is available in [Table 1](#).

Treatment with inhaled molgramostim will be given at a dosage of 300 µg once daily for 48 weeks. All subjects in the trial initially consented to 24 weeks of treatment. All enrolled subjects continuing with 48 weeks of treatment will re-consent and follow the visits schedule as described above.

Subjects that do not wish to continue to 48 weeks of treatment will end treatment after 24 weeks (visit 8) and will attend the follow-up visit 12-weeks later as per the visit schedule outlined in Protocol Version 2.0 or 3.0.

Subjects who complete the initial 24-week treatment period prior to the approval of Protocol Version 4.0 will proceed to the 12 week follow up as per the visit schedule in Protocol Version 2.0 or 3.0. Once Protocol Version 4.0 is approved they will be asked to re consent and re-initiate treatment. This will occur at the next trial visit or at an unscheduled visit. These subjects will not receive the whole 48-week treatment. They will receive treatment for an additional 24 weeks minus the number of weeks that they have been in follow up.

Subjects that do not wish to re consent and re initiate treatment will stay in follow up and attend the follow-up visit as per the visit schedule outlined in Protocol Version 2.0 or 3.0.

At Baseline and at Weeks 4, 12, 24, 32 and 40 (Visits 2, 3, 5, 8, 10 and 12), dosing will take place in the clinic after blood sampling. A data review was conducted after the first 6 subjects had completed 12 weeks of treatment. If safety concerns or poor tolerability were identified in this review, the review committee might decide on less frequent dosing for subsequent subjects

in the study. The review was conducted on 16 September 2018 and concluded that there were no safety issues of significant concern and the dose was unchanged. In order to obtain more robust treatment responses it was decided to extend the treatment duration from 24 to 48 weeks. Any changes to the conduct of the study such as change of dose, dose regimen or duration will be documented in a protocol amendment.

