### **11.5. Administration**

The PARI eFlow nebulizer system (PARI Pharma GmbH, Germany) will be used to administer the IMP. The eFlow Nebulizer Handset is a single subject use, reusable electronic nebulizer. It includes a fine particle aerosol generator (perforated vibrating membrane) defined by a 30L mesh and an aerosol chamber that can produce aerosols with high density of active drug, precisely defined droplet size and a high proportion of respirable droplets.

All subjects, investigators and trial nurses will be trained in IMP administration and medical device maintenance procedure. The training of the subjects will be arranged prior to

administration of the subject's first dose of IMP and checked in clinic on first dosing. The subject will also receive written instructions.

The subject will administer the first dose of IMP at the Baseline visit (Visit 2) under the supervision of trial personnel.

During the treatment period at Weeks 4, 12, 24, 32 and 40 (Visits 3, 5, 8, 10 and 12), subjects will be asked not to take their study treatment prior to the clinic visit because blood samples for laboratory testing will be taken. At these visits dosing will take place in the clinic after the blood samples have been taken. The subject should be instructed to take the last dose the day before the 48-week visit (Visit 14).

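### Sputum baseline pools Visit 2 samples that are by default collected at home after the first dose, so baseline smear status and grades can rest on on-drug samples in up to about 24 of 30 subjects

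*SAP*

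**What the plan says.** SAP 3.3.3 gives sputum its own baseline rule: "For sputum data, baseline will be derived from the combined pre-treatment visits (i.e. Screening and Baseline". Within that pool the status rule is "where at least one positive sample will be assigned as positive as baseline", and "For gradings, the most severe/highest grade will be used". For all other parameters the same section says "baseline will be defined as the last available assessment prior to first study drug administration".

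The sampling schedule is in Table 1 footnote c of the protocol: "Three samples, preferably on consecutive days, will be collected". For clinic visits, with Visit 2 in the list, Protocol 8.1 says "subjects will be asked to collect two additional sputum samples at home, preferably on the consecutive days after the site visit"; Protocol 12.2 and SAP 2.1 repeat this. SAP 2.1 adds that when the study began only one sample was required at Visits 2 to 7.

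On dosing, Protocol 11.5 says "The subject will administer the first dose of IMP at the Baseline visit (Visit 2) under the supervision of trial personnel", and Protocol 8.1 says "Treatment with inhaled molgramostim will be given at a dosage of 300 µg once daily for 48 weeks".

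**The concern.** SAP 3.3.3 calls Visit 2 a pre-treatment visit, but treatment starts there. The two home samples belonging to that visit are planned for days when the subject is already on daily drug. Nothing in the sputum rule removes them, although the next sentence of the SAP requires a pre-dose value for everything else. SAP Table 3 itself files the Baseline Visit under the treatment epoch.

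Three sets of results depend on this baseline. Smear conversion is assessed only in subjects who were smear positive at baseline, so baseline status fixes its denominator. Baseline smear grade and baseline culture grade are the reference for the two bacterial-load endpoints. In an uncontrolled trial, change from baseline is the only comparison these load endpoints have, so the reference should be free of study drug.

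**Working it through.** The plan gives no figure on this point to reproduce. The check is one of timing, followed by arithmetic for scale.

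**1. Order of events at Visit 2 (current schedule)**

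| Event | Planned timing | Source |
|---|---|---|
| Clinic sputum sample | Visit 2; order relative to dosing not stated | Protocol 8.1, 12.2 |
| First dose | Visit 2, in clinic | Protocol 11.5 |
| Two home samples | Preferably the days after Visit 2 | Protocol 8.1, 12.2; SAP 2.1 |

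By default 2 of the 3 Visit 2 samples, and 2 of up to 6 pooled baseline samples (3 Screening + 3 Visit 2), are post-dose. The rule of sampling before dosing covers blood only (Table 1 footnotes d and g; Protocol 12.14), so the clinic sputum sample is not guaranteed to be pre-dose either.

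**2. Who is affected**

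The first 6 subjects had completed 12 weeks by the review of 16 September 2018 (Protocol 8.1). Counting back 84 days gives a Visit 2 no later than 24 June 2018; with the 7-day window (77 days), 1 July 2018. Version 3.0, which brought in three samples at every visit, is dated 22 August 2018. At least 6 of 30 (20%) therefore had only one required Visit 2 sample, and at most 30 − 6 = 24 are exposed.

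**3. Smear status: six samples against four**

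Assumptions: independent samples, per-sample positivity *s* (not given in the documents, so shown as a range) and no drug effect.

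P(positive only through the two home samples) = (1 − s)^4 × [1 − (1 − s)^2]

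Share of baseline positives = that probability ÷ [1 − (1 − s)^6]

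| s | Probability | Share of baseline positives | Expected number if all 24 had this s |
|---|---|---|---|
| 0.05 | 0.8145 × 0.0975 = 0.079 | 30% | 1.9 |
| 0.10 | 0.6561 × 0.19 = 0.125 | 27% | 3.0 |
| 0.20 | 0.4096 × 0.36 = 0.147 | 20% | 3.5 |
| 0.30 | 0.2401 × 0.51 = 0.122 | 14% | 2.9 |
| 0.50 | 0.0625 × 0.75 = 0.047 | 5% | 1.1 |
| 0.70 | 0.0081 × 0.91 = 0.007 | 1% | 0.2 |

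The probability peaks at 4/27 = 0.148 near s = 0.18, so 10–30% is the range where the effect is largest. If the clinic sample cannot be shown to be pre-dose, the formula becomes (1 − s)^3 × [1 − (1 − s)^3]: 0.729 × 0.271 = 0.198, 0.512 × 0.488 = 0.250 and 0.343 × 0.657 = 0.225 at s = 0.10, 0.20 and 0.30.

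**4. Grades: the highest-of-pool rule**

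For illustration, take five equally likely grades, independent samples, no drug effect, and a worst-of-3 grade at the later visit. SAP 9.3.2.4 states the worst-grade rule for culture; I assume it for smear. With F(g) = 0.2, 0.4, 0.6, 0.8, 1:

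P(apparent decrease) = Σ [F(g)^k − F(g−1)^k] × F(g−1)^3

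- k = 6: 0.000 + 0.003 + 0.047 + 0.378 = 0.43
- k = 4: 0.000 + 0.007 + 0.060 + 0.302 = 0.37
- k = 3: 0.000 + 0.010 + 0.064 + 0.250 = 0.32

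The lean towards a decrease comes from comparing more samples at baseline than at the visit. Dropping the two home samples (6 to 4) removes about half of the excess over 0.32.

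**The case against.** The strongest reply is that one or two doses are unlikely to change sputum, and the documents contain no evidence that they do. If there is no early effect, a home sample is as valid as a pre-dose one, and a positive smear on the day after Visit 2 correctly identifies an intermittently positive subject. The affected endpoints are secondary and descriptive, and SAP 9.3.2 lists microscopy and culture per sample. The home timing is a preference, and at least the first 6 subjects had no required home sample at Visit 2. SAP 9.3.2.4 also notes that culture grade is not available from the UK laboratory, so that endpoint concerns Australian samples only. All of this stands, and it limits scope and weight. None of it makes the pre-treatment label correct or supplies a pre-dose cut-off.

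A reader might infer more than the documents support:

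- **That baseline is biased towards improvement because nebulised treatment provokes cough.** The phase I figures (70% on drug, 67% on placebo; Protocol 6.1) are adverse-event rates in healthy adults and say nothing about sputum quality. Dosing is daily, so any such effect would be present in later samples too. An early antimycobacterial effect would push the other way.
- **That the 12–15% measures contamination by drug.** It assumes no drug effect, so it measures what six samples detect beyond four.
- **That the one-way movement of baseline is caused by post-dose timing.** It is caused by the any-positive and highest-grade rules; two further pre-dose samples would do the same.
- **That the primary endpoint is compromised.** A positive Screening culture is required for entry (Protocol 8.1), so baseline culture status does not depend on Visit 2, and conversion is judged over treatment-period visits (SAP 9.2.1).

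**Conclusion.** The point holds as one of definition. Followed as written, SAP 3.3.3 admits on-drug samples to the sputum baseline of at most about 24 of 30 subjects, contrary to its own label and to the rule it sets for every other parameter. The smear-conversion denominator and the baseline smear and culture grades are exposed; the primary culture endpoint largely is not. How far, and in which direction, early dosing changes these samples cannot be determined from the documents.

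What can be sized is the classification effect of the two extra samples. Under independence and no drug effect, 12–15% of subjects with 10–30% per-sample positivity would be smear positive at baseline only through the home samples. The figure is about 8% at 5% positivity, 5% at 50% and under 1% at 70%. This matters for secondary, exploratory results and is cheap to correct.

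**What to change.** In SAP 3.3.3, define sputum baseline from samples collected before first study drug administration: the Screening samples plus any Visit 2 sample documented as pre-dose. Report the current pooled definition as a sensitivity analysis. The rule must work sample by sample. SAP 8.1.1 captures date and time of clinic dosing, but neither document says that sputum collection time is recorded. Home samples can be classified by date; the Visit 2 clinic sample may not be classifiable.

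For subjects still to be enrolled, state in Table 1 footnote c and Protocol 12.2 that Visit 2 sputum is collected before the first dose, with collection date and time recorded.

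The cost is one SAP sentence, a footnote and a matching line in 12.2, with no extra samples. Affected subjects lose up to two baseline samples, or three if the clinic sample cannot be shown to be pre-dose. Slightly fewer will then count as smear positive, so the smear-conversion denominator is somewhat smaller. The change does not remove the asymmetry of the highest-grade rule, which should be stated when grade changes are interpreted.

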9.3.2 *Secondary Endpoints*

9.3.2.1 *Sputum Smear Conversion (Primary)*

Sputum smear conversion will be evaluated and presented in the same way as the primary endpoint for culture conversion.

9.3.2.2 *Sputum Smear Conversion (Sensitivity)*

In a sensitivity analysis, smear conversion will be re-defined as requiring at least 2 samples are available from each of the three consecutive visits. Sputum smear conversion rates and time to smear conversion will be analysed as part of this sensitivity analysis.

9.3.2.3 *Mycobacterial Microscopy Grading*

Mycobacterial microscopy data will be listed for each sample, including AFB positivity and AFB semi-quantitative grading. The listing will also include the overall visit AFB positivity and grading statuses. Laboratory grading terminology will be re-named as detailed in Table 4.

Table 4: *Mycobacterial Microscopy Grading*

SNP	RBH	Cross-Tabulation
No acid fast bacilli seen	No AFB Seen	Negative
Acid fast bacilli – occasional	Scanty AFB Seen +/-	Scant
Acid fast bacilli +	Moderate AFB Seen 1+	1+
Acid fast bacilli ++	Moderate AFB Seen 2+	2+
Acid fast bacilli +++	AFB Seen 3+	3+
Acid fast bacilli ++++		4+

The number of subjects who decrease over the scale (and proportion out of the number per group) will be presented with 95% exact binomial confidence intervals.

A summary table will present continuous descriptive statistics of grade for each scheduled visit.

9.3.2.4 *Mycobacterial Culture Grading*

Mycobacterial culture data will be listed for each sample, including culture positivity, culture semi-quantitative grading, time to detection in liquid media (MGIT) and organisms isolated. The listing will also include the overall visit AFB positivity and grading statuses.

The following is noted:

- MGIT and semi-quantitative grading will need to be extracted from the Comment column in the SNP data transfer.
- Semi-quantitative grading is not available for mycobacterial culture data from RBH.

For each scheduled visit, the number of subjects (and proportion out of the number per group) who report a decreased culture grade compared to Baseline will be presented with 95% exact binomial confidence intervals. Where multiple samples were taken at a visit, the worst grade will be used for comparison to Baseline.

A figure will present the mean change from baseline of semi-quantitative sputum culture grades, with error bars representing the standard deviation.

9.3.2.5 *Symptom Scores*

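### Sputum baseline grade is the highest of up to six samples over two visits, but is compared with the worst of at most three at one later visit, so the grade-change summaries lean towards improvement

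*SAP*

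**What the plan says.** **Baseline.** SAP 3.3.3 derives the sputum baseline from Screening and Visit 2 together, "where at least one positive sample will be assigned as positive as baseline. For gradings, the most severe/highest grade will be used". All other parameters take the last assessment before the first dose.

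**Later visits, culture (SAP 9.3.2.4).** "Where multiple samples were taken at a visit, the worst grade will be used for comparison to Baseline". At each scheduled visit, the subjects "who report a decreased culture grade compared to Baseline will be presented with 95% exact binomial confidence intervals". Also, "A figure will present the mean change from baseline of semi-quantitative sputum culture grades".

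**Later visits, smear (SAP 9.3.2.3).** "The number of subjects who decrease over the scale (and proportion out of the number per group") is reported with an exact 95% interval, and grade is summarised descriptively by visit. An overall visit grade is listed, but the rule that forms it is not given.

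**Sample counts.** Protocol Table 1, footnote c, gives three samples at every visit. SAP 2.1 adds that early on only one was required at Visits 2 to 7.

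**Coverage.** "Semi-quantitative grading is not available for mycobacterial culture data from RBH", so culture grade comes from the Australian laboratory only.

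**What shows increases.** Protocol 13.2 planned 5-by-5 tables of baseline against later grade. SAP 13 replaces them with other summaries. The sensitivity analyses in SAP 9.3.1.2 and 9.3.2.2 cover conversion, not grade change.

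**The concern.** A maximum over more samples is higher on average than a maximum over fewer from the same subject. Here the larger set is always on the baseline side, so part of any apparent fall in grade is produced by the definition. Entry also requires a positive Screening culture, and Screening feeds the baseline, which adds regression to the mean for culture.

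Reduction of bacterial load is a secondary objective, there is no control arm, and Protocol 6.3 says the pilot will inform the further phase II programme. Only decreases receive a proportion and an interval, so the increases that would give a chance fluctuation away are not shown beside them. SAP 14 also lists grade change as an interim endpoint, without a decision rule.

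**Working it through.** The plan states no figure on this point, so there is none to reproduce. The question is what the planned summaries would show with no drug effect.

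**Inputs from the documents.** Three samples per visit (Protocol Table 1); one at Visits 2-7 for early subjects (SAP 2.1); maximum over two visits at baseline (SAP 3.3.3); maximum within one visit for culture later (SAP 9.3.2.4); five smear grades in the protocol, six in SAP Table 4.

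**Assumptions not in the documents.** The grade distribution, the share of negative samples, and how variation divides between subjects, visits and samples.

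**Step 1: an example to check by hand.** Take five equally likely grades and independent samples, so F(k) = k/5 and P(maximum of n ≤ k) = F(k)^n.

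- P(decrease) = Σ [F(k)^6 − F(k−1)^6] × F(k−1)^3 = 0.0000 + 0.0027 + 0.0465 + 0.3778 = 0.427 (k = 2 to 5)
- P(increase) = Σ [F(k)^3 − F(k−1)^3] × F(k−1)^6 = 0.0000 + 0.0006 + 0.0138 + 0.1279 = 0.142
- Mean change = −Σ [F(k)^3 − F(k)^6] over k = 1 to 4 = −(0.0079 + 0.0599 + 0.1693 + 0.2499) = −0.487 grade
- Three against three: 0.324 each way, mean change 0

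**Step 2: correlated samples.** Simulation of 400,000 subjects per setting. A latent normal value has a subject share of variance 0.5-0.95 and a visit share 0-0.3. There are five or six grades, with positives split equally; 20% of samples are negative, and a positive Screening sample is required.

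| Baseline v later visit | When it applies | Decrease | Increase | Mean change |
|---|---|---|---|---|
| 6 v 3 | current schedule, all samples | about 21-50% | 6-18% | −0.15 to −0.68 |
| 4 v 3 | Visit 2 home samples not counted | 17-45% | 9-23% | −0.08 to −0.48 |
| 4 v 1 | early subjects, three Screening samples | 38-67% | 4-14% | −0.36 to −1.30 |
| 2 v 1 | early subjects, one Screening sample | 28-56% | 8-19% | −0.21 to −0.86 |
| 1 v 1, 2 v 2, 3 v 3 | Visit 2 only, matched | 13-37% | 13-37% | 0.00 |

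The 4 v 3 row arises because Protocol 12.2 prefers home samples on the days after the visit and Protocol 11.5 gives the first dose at Visit 2. It takes the clinic-day sample to be pre-dose. The documents do not state the original number of Screening samples or how many subjects used the early schedule.

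Without the entry condition, which is the nearer case for smear because entry is on culture, 6 v 3 gives 19-48% v 6-19% and −0.12 to −0.61. With 50% of samples negative and entry required, it gives 29-58% v 8-17%.

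**Step 3: what holds for any scale.** Let A, B and C be the worst grades at Screening, Visit 2 and a later visit, exchangeable and with equal sample counts. Let u be the probability that one visit alone is highest, and t the probability that exactly two tie for highest. Then P(increase) = u/3 and P(decrease) = 2u/3 + t/3, so their ratio is 2 + t/u, at least 2. Requiring A to be positive removes equal amounts from both and cannot lower the ratio.

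**Step 4: where that ratio fails.** In 4 v 3 the counts are unequal and the ratio is 1.6-2.1. If Screening and Visit 2 share short-term variation (correlation 0.5-1.0 between their visit effects, subject share 0.5, visit share 0.3), 6 v 3 gives 41-48% v 18-24%, and the ratio can fall just below 2. The direction is unchanged in both cases.

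**The case against.** This is a 30-subject exploratory pilot with descriptive analysis and no threshold on grade change. Sampling error is large: an exact 95% interval for 12 of 30 is 23-59%, and for 6 of 15 it is 16-68%. A pooled worst grade also has a purpose for culture. Given the entry rule, no subject starts at the bottom of the scale with no room to fall. All of that stands, and it limits the practical weight. It excuses imprecision, though, not an error whose direction is known in advance.

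A reader might infer that the built-in fall cannot be told apart from a drug effect at all. The documents do not support that. SAP 9.3.2.3 summarises smear grade by scheduled visit, and Screening and Visit 2 are separate visits in SAP Table 3, so Visit 2 can be set beside later visits if the table is laid out that way. Every sample is listed. For subjects with three samples throughout, the artefact is a roughly constant step, so the course from Week 4 to Week 48 is not distorted by it. These are partial checks: they leave the headline proportions and the culture figure as they are, and for early subjects the step changes when the sample count changes.

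SAP 9.2.2 says culture grade change draws on time to positivity and exploratory quantitation. That leaves the scale unclear, but the argument holds for any ordered scale.

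**Conclusion.** The concern holds for the culture grade-change summaries: the proportion decreasing and the mean-change figure lean towards improvement without any drug effect. The direction is certain unless a subject's grades never vary. The size is illustrative, because variance shares, grade distribution and share of negatives are assumed; the range runs from modest (4 v 3) to large (4 v 1).

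Three stronger readings go too far:

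- **That decreases must outnumber increases by 2 to 1.** This is a bound only for exchangeable visits with equal sample counts, and step 4 shows two plausible departures.
- **That smear grade is shown to be biased.** It leans the same way if the visit grade is the worst grade or milder, but SAP 9.3.2.3 does not state the rule.
- **That the primary result is affected.** Culture conversion (SAP 9.2.1) depends on negative samples at three consecutive visits during treatment and uses no baseline grade.

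The change should be made, but the plan does not fail without it.

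**What to change.** 1. For grade change, take baseline from Visit 2 and compare it with each later visit by the worst grade over the same number of samples: the first k of each visit, where k is the smaller count available.
2. Add a first-sample-only (1 v 1) sensitivity analysis. At Weeks 28, 36 and 44 this compares a clinic-day sample with a home sample.
3. State the same worst-grade rule for the smear visit grade in SAP 9.3.2.3.
4. Report the number and proportion who increase beside those who decrease. This is needed even with equal windows, since the matched row above shows many decreases by chance.
5. Keep the pooled-maximum baseline only as a labelled sensitivity analysis.

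**Cost.** SAP wording and a little reprogramming: one derivation, two tables and one figure.

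**Downsides to state in the SAP.**
- Two of the three Visit 2 samples are scheduled after the first dose.
- Subjects without a Visit 2 sample drop out of these tables, and some samples go unused.
- The reported decrease will look less favourable.
- Subjects negative at Visit 2 cannot decrease, so their number should be shown. In these settings they are about 3-7% in 3 v 3 and 7-18% in 1 v 1 with 20% of samples negative, and about 6-22% and 16-40% with 50% negative.
- If Screening and Visit 2 are serially correlated, a small lean remains in 3 v 3: 33-37% decreasing v 29-34% increasing, mean change −0.05 to −0.11.
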